3.4 Dose Modifications

All toxicity grades below are described using the NCI Common Terminology Criteria for Adverse Events (CTCAE) version 5.0.

All appropriate treatment areas should have access to a copy of the CTCAE version 5.0. A copy of the CTCAE version 5.0 can be downloaded from the CTEP website

(http://ctep.cancer.gov/protocolDevelopment/electronic_applications/ctc.htm)

Dose Modifications and Dose Delays

Treatment can be modified or terminated based on toxicity as described in Table 1. For eye, skin/nail, dry mouth/mucositis, liver, and phosphate toxicity, specific recommendations in the management guidelines are provided below.

Table 1: Dose Modification Guidelines

Toxicity Grade	Action	Dose Modification After Resolution of Adverse Event
1	None	Continue same dose
2	None or consider interruption	If interrupted, restart at same dose or 1 dose lower, if necessary.
3	Interrupt drug	Restart at 1 or 2 doses lower if recovery (to \leq Grade 1 or back to baseline for non-hematologic toxicity) is within 28 days. Discontinue drug if unresolved for >28 days.
4	Interrupt drug or discontinue	Discontinue*

For general toxicity management:

- Subjects with any grade of toxicity (Grade 1 to 4) should be provided symptomatic treatment when applicable.
- Subjects should follow the guidelines in Table 2 for dose reduction recommendations and may have more than 1 dose reduction.
- If JNJ-42756493 (erdafitinib) must be withheld for more than 28 days for a drug-related adverse event that fails to resolve to acceptable level (e.g., \leq Grade 1 non-hematologic toxicity or back to baseline), treatment with JNJ-42756493 (erdafitinib) should be discontinued with the exception noted below.*
- If the subject achieves calcium-phosphate product $> 70 \text{ mg}^2/\text{dL}^2$ for 2 consecutive weeks despite phosphate lowering therapy or $> 90 \text{ mg}^2/\text{dL}^2$ any time during treatment despite phosphate lowering therapy, JNJ-42756493 (erdafitinib) should be withheld until recovery to calcium-phosphate product $< 55 \text{ mg}^2/\text{dL}^2$. Treatment may be reintroduced at the first reduced dose level.
- In all cases of clinically significant impaired wound healing or imminent surgery or potential bleeding complications, it is recommended that dose administration be interrupted, appropriate clinical laboratory data be carefully monitored, and supportive therapy administered, where applicable. Dose

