Grade 1: Asymptomatic or mild symptoms; clinical or diagnostic observations only Or abnormal Amsler grid test	
Refer for an ophthalmologic examination. If an ophthalmologic exam cannot be performed within 7 days, withhold treatment of JNJ-42756493 until an examination can be performed.
 
If there is no evidence of eye toxicity on ophthalmologic examination, continue JNJ-42756493 therapy at the same dose level.
 
If diagnosis from ophthalmologic examination is keratitis or retinal abnormality such as central serous retinopathy (CSR)/ retinal pigment epithelial detachments (RPED), withhold JNJ-42756493 until signs and symptoms have resolved.
 
If toxicity is reversible (complete resolution or stabilization and asymptomatic) in 4 weeks according to ophthalmologic examination, resume JNJ-42756493 therapy at the next lower dose level after consultation with the medical monitor.^a
 
Monitor for recurrence every 1 to 2 weeks for a month and as clinically appropriate thereafter. If there is no recurrence then re-escalation can be considered in consultation with the medical monitor.^a
	
Refer the subject for an ophthalmologic examination.
 
For retinal pathology perform OCT as appropriate and consider referral to a retinal specialist for further evaluation.
 
Follow specific treatment per the ophthalmologist's recommendation.

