Grade 2: Moderate; minimal, local or noninvasive intervention indicated; limiting age appropriate instrumental ADL	
Immediately withhold JNJ-42756493 therapy.
 
If there is no evidence of drug-related corneal or retinal pathology on ophthalmologic examination, withhold JNJ-42756493 until signs and symptoms have resolved. Resume JNJ-42756493 therapy at the next lower dose level.
 
If diagnosis from ophthalmologic examination is keratitis or retinal abnormality such as CSR/RPED, withhold JNJ-42756493 until signs and symptoms have resolved, stabilized, or subject is lost to follow-up or withdraws consent (which ever happens first).
 
If toxicity is Grade 2 and reversible (complete resolution or stabilization and asymptomatic) within 4 weeks according to ophthalmologic examination, resume JNJ-42756493 therapy at the next lower dose level after consultation with the medical monitor.
	
Refer subject to an ophthalmologist for evaluation with an ophthalmologic examination.
 
For retinal pathology, perform OCT as appropriate and consider referral to a retinal specialist for further evaluation.
 
Follow specific treatment per the ophthalmologist's recommendation.

Grade 3: Severe or	If the toxicity is Grade 3, report as a serious adverse	

Table 9: Guidelines for Management of Eye Toxicity

Grade and Definition	Study Drug Management	Medical Management
medically significant but not immediate sight-threatening; hospitalization or prolongation of existing hospitalization indicated; disabling; limiting self-care ADL	event and permanently discontinue JNJ-42756493. If however the toxicity is Grade 3 and reversible (complete resolution or stabilization and asymptomatic) within 4 weeks and the subject is having clinical benefit, and the investigator and the sponsor's medical monitor agree that re-starting drug is in the best interest of the subject, then JNJ-42756493 therapy may be resumed at 2 dose levels lower if appropriate. ^a Monitor for recurrence using appropriate investigations every 1 to 2 weeks for a month and as clinically appropriate thereafter. For cases of recurrence consider permanent discontinuation.	

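### Table 9, Grade 1 row: the hold and restart rules give opposite instructions for a corneal or retinal sign that persists but is stable and asymptomatic

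*Protocol*

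**What the plan says.** All of the text is in Protocol section 3.4 (Dose Modifications), Table 9, the guidelines for eye toxicity.

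- **Grade 1 definition.** "Grade 1: Asymptomatic or mild symptoms; clinical or diagnostic observations only Or abnormal Amsler grid test". An event can therefore be Grade 1 without any symptom, as a finding on examination only.
- **Grade 1 hold.** If the examination shows keratitis or a retinal abnormality such as central serous retinopathy (CSR) or retinal pigment epithelial detachment (RPED), the site is to "withhold JNJ-42756493 until signs and symptoms have resolved".
- **Grade 1 restart, next paragraph of the same cell.** "If toxicity is reversible (complete resolution or stabilization and asymptomatic) in 4 weeks according to ophthalmologic examination", then "resume JNJ-42756493 therapy at the next lower dose level after consultation with the medical monitor". Footnote a is attached to this instruction.
- **Grade 2 hold, same diagnoses.** "withhold JNJ-42756493 until signs and symptoms have resolved, stabilized, or subject is lost to follow-up or withdraws consent".
- **Grade 2 and Grade 3 restart.** The same parenthetical definition of reversible is used as in Grade 1.
- **General rule, text after Table 1.** Treatment should be discontinued, with a stated exception, if drug "must be withheld for more than 28 days for a drug-related adverse event that fails to resolve to acceptable level". The example given of an acceptable level is Grade 1 or lower for non-hematologic toxicity, or baseline.

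**The concern.** The hold sentence sets one end point: both signs and symptoms gone. The restart sentence sets another, with stabilization without symptoms as an alternative to complete resolution. A site that applies the first keeps withholding drug while any sign remains. A site that applies the second may restart at a reduced dose with the sign still there. Both would be following the protocol.

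The conflicting state is an ordinary one for this grade. A Grade 1 lesion may have no symptoms when it is found, so one that is simply unchanged at re-examination can be stable and asymptomatic without having improved.

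At stake are a safety instruction for an adverse event of special interest, and the consistency across sites of drug exposure and dose modification. Patients with the same findings could have different interruption lengths and dose histories because of which sentence was followed.

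**Working it through.** The point rests on wording, so no arithmetic applies and there is no figure in the plan to reproduce. I set the two Grade 1 rules side by side and applied each to the states a lesion can be in at re-examination within the 4 weeks.

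**Rule A (hold):** drug is withheld until signs and symptoms have both resolved.

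**Rule B (restart):** drug is resumed one level down, after consulting the medical monitor, if the event is reversible. The parenthesis can be read two ways:
- B1: complete resolution, or else stabilization together with no symptoms.
- B2: either complete resolution or stabilization, and in both cases no symptoms.

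| State at re-examination | Rule A | Rule B (B1 and B2) | Result |
|---|---|---|---|
| 1. No sign, no symptoms | Hold ends | Met, restart | Agree |
| 2. Symptoms persist | Hold continues | Not met | Agree |
| 3. No symptoms, sign present and still improving | Hold continues | Not met | Agree |
| 4. No symptoms, sign present and stable | Hold continues | Met, restart | **Conflict** |

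State 4 conflicts under B1 and B2 alike, so settling the grammar of the parenthesis does not remove it. The Grade 1 definition puts an event that is asymptomatic at onset and unchanged at re-examination into state 4. The protocol does not define stabilization; I take its ordinary meaning, no longer changing.

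**Does the second sentence merely explain what resolved means?** The table's own usage says not. Stabilization stands as an alternative to complete resolution in the restart definition of Grades 1, 2 and 3. The Grade 2 hold lists resolved and stabilized as separate end points, and the Grade 4 monitoring instruction also separates them.

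**Comparison with Grade 2.** For a stable, asymptomatic sign the Grade 2 hold ends, because stabilization suffices, and the Grade 2 restart test is met. The two Grade 2 sentences agree in this state. In Grade 1 they do not. On the hold sentence alone, the milder grade has the stricter end point. The restart test is the same in both rows.

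**Does other text settle it?**
- The general 28-day rule does not: its example of an acceptable level is Grade 1 or lower, which a persisting Grade 1 lesion already meets.
- The Grade 1 row does not say what follows if a sign is still present after 4 weeks.
- Footnote a governs who must agree to re-introduction (medical monitor and IRB in writing, patient by re-consent). It does not say what counts as recovery.

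**The case against.** The strongest reply is that the restart definition is uniform across Grades 1 to 3 and is the specific, time-limited rule. A clinician reading in order may take the hold sentence as general and the next paragraph as qualifying it. That is a workable reading, but the text does not impose it: the hold sentence is unqualified in Grade 1, and the Grade 2 row shows how the authors write a hold that may end at stabilization.

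The second reply is that a site does not restart on its own reading. Restart needs an ophthalmologic examination and consultation with the medical monitor, and footnote a adds written permission and re-consent. Table 9 is headed as guidelines, and the notes to Figure 1 in section 3.1 leave interruptions to the investigator as clinically indicated. This stands in part: one medical monitor should limit variation between sites, so the fair statement is that sites could diverge, not that they will. The monitor is still given two criteria.

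A reader might infer more than the documents support:
- **That the number of affected patients can be estimated** by applying the adverse event list's frequency for CSR to the accrual goal of 35. That list gives a grouped term, not restricted by grade or course; it includes, for example, retinal oedema and vitreous detachment. The conflict reaches only Grade 1 events with a persistent, stable, asymptomatic sign. The assumed 30% of patients needing follow-up ophthalmological examination counts examinations, not events in this state.
- **That event outcome or reversibility data become uninterpretable.** Table 9 governs study drug management. Nothing shown makes its term reversible an outcome category, and adverse event reporting is referred to the Master Protocol, which is not at hand.
- **That the loss-to-follow-up and consent wording in the Grade 2 hold is part of the problem.** A patient who is lost or has withdrawn will not restart, so it changes no restart decision.

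**Conclusion.** The point holds as a contradiction between two adjacent operative sentences in the Grade 1 row of Table 9. It is confined to one of the four states considered: a corneal or retinal sign that persists, is stable and causes no symptoms. There one sentence continues the hold and the other directs restart at a reduced dose. In the other three states the sentences agree.

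Its size in patients is unknown, because the documents give no frequency for this state. No sample size, error rate or power is affected. What can be affected is the hold-or-restart decision for individual patients, and through it the consistency of exposure and dose-modification data across sites. The existing safeguards reduce that risk without removing the contradiction.

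It would overstate matters to say that Grade 1 events are managed more strictly than Grade 2 events as a whole. That is true of the hold sentence only.

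The conclusion rests on stabilization having its ordinary meaning, and on resolved and stabilized being distinct, as the table's separate listing of them indicates. It takes no position on which criterion is clinically right.

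**What to change.** The sponsor should reconcile the hold and restart sentences in the Grade 1 row of Table 9, and align them with the Grade 2 row, so that one recovery criterion governs both the end of the hold and the restart. The text should state expressly whether a persistent, stable, asymptomatic sign meets that criterion. The choice of criterion is the sponsor's.

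The cost is a wording change to two rows of one table. No examination is added, since the restart decision already depends on an ophthalmologic examination.

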3.5 Supportive Care

All supportive measures consistent with optimal patient care will be given throughout the study.

3.6 Duration of Agent-specific treatment

In the absence of treatment delays due to adverse event(s), treatment may continue until one of the following criteria applies:

- **Extraordinary Medical Circumstances:** If at any time the constraints of this protocol are detrimental to the patient's health, protocol treatment should be discontinued. In this event submit forms according to the instructions in the MATCH Forms Packet.

- Patient withdraws consent.
- Patient experiences unacceptable toxicity.
- Non-protocol therapies are administered.
- Disease progression

3.7 Duration of Follow-Up

Refer to the MATCH Master Protocol for specifics on the duration of follow-up.

Rev. Add16 4. Study Parameters

4.1 Therapeutic Parameters for JNJ-42756493 (Erdafitinib) Treatment

NOTE: In addition to the study parameters listed in the MATCH Master Protocol, the below parameters must also be performed for patients receiving JNJ-42756493 (erdafitinib) treatment.

NOTE: All assessments required prior to registration to treatment should be done \leq 4 weeks prior to registration to Steps 1, 3, 5, 7, excluding the radiologic evaluation and electrocardiogram (ECG).

Test/Assessment	Prior to Registration to Treatment	Treatment			End of Treatment	Follow Up ^F
		Every Cycle, prior to treatment	Cycle 1 Day 15	Every 2 Cycles		
H&P, Weight, Vital signs ^A	X	X ^J	X			X
Performance status	X	X ^J	X			X
CBC w/diff, plt ^B	X	X ^J	X			X
Serum chemistry ^B	X	X ^J	X			X
Radiologic evaluation ^D	X		X ^D			X ^F
β -HCG ^C	X					
Toxicity Assessment ^G		X	X	X	X	X ^F
Pill Count/Diary ^H			X			X
ECG ^K	X	X ^I				
Ophthalmologic exam ^L	X	X			X	
Phosphate Levels ^M			X			
Tumor biopsy and blood sample for MATCH Master Protocol ^E				X	X	X

- History and physical, including vital signs and weight at the start of each cycle (up to 3 days before start of new cycle).
- Albumin, alkaline phosphatase, total bilirubin, bicarbonate, BUN, calcium, creatinine, glucose, phosphorus, potassium, SGOT[AST]^J, SGPT[ALT]^J, sodium, magnesium and serum tumor markers (including LDH, PSA if appropriate). Serum tumor markers are not required on Cycle 1, Day 15. For eligibility purposes, participants with creatinine levels above institutional normal, Cockcroft-Gault will be used to calculate creatinine clearance. CBC w/diff, platelets and serum chemistries should be performed on cycle 1, day 1 (or up to 7 days prior), and at the start of each subsequent cycle (up to 3 days before start of new cycle). CBC with differential will be performed more frequently in patients with grade 4 neutropenia or thrombocytopenia until resolution to \leq grade 3. CBC and serum chemistries are only required in follow-up until values return to pre-treatment levels or until progressive disease.
- Blood pregnancy test (women of childbearing potential) required prior to beginning treatment.

D. Disease measurements are repeated every 2 cycles for the first 26 cycles, and every 3 cycles thereafter until PD or start of another MATCH treatment step. The baseline evaluation should be performed as closely as possible to the beginning of treatment and never more than 6 weeks before registration to treatment step. For multiple myeloma patients, please refer to Section 6.4 of the MATCH Master Protocol for additional information on myeloma response criteria and the required disease assessments. Documentation (radiologic) must be provided for patients removed from study for progressive disease.

E. Additional blood specimens and/or biopsies are to be submitted from consenting patients per Section 9.3.2 of the MATCH Master Protocol. Submit at the following time points, as applicable:

- Blood specimens are to be submitted at the end of Cycle 2 (prior to start of Cycle 3 treatment). If patient progresses or treatment is discontinued prior to Cycle 3, collect the blood at that time instead. On-treatment kits for blood sample collections will be automatically shipped to sites upon registration to the treatment step.
- Screening biopsies for additional aMOI assessments after registration to appropriate screening step, if applicable (Step 2 or Step 4).
- At end of all MATCH study treatments, blood specimens and/or research biopsy after consent and registration to Step 8

Please refer to Section 4 of the MATCH Master Protocol to determine whether the patient proceeds to the next screening step or to follow-up (with a potential end of treatment biopsy for research purposes on Step 8). Samples are to be submitted as outlined in Section 9 of the MATCH Master Protocol. To order Step 2/4 Screening or Step 8 kits, complete the EAY131 Collection and Shipping Kit Order Form (See Appendix XII of the MATCH Master Protocol) and fax to [contact].

F. Every 3 months if patient is < 2 years from study entry, and every 6 months for year 3. Toxicity assessments and radiologic evaluations are not required to be done during Follow Up if progression has been previously reported; however if an adverse event occurs post treatment that meets the SAE reporting requirements, it still must be reported via CTEP-AERS, even if progression has occurred.

G. Site personnel should evaluate for toxicity and discuss treatment compliance with the patient in order to ensure the medication is taken correctly; this evaluation must be conducted in person. The Toxicity Assessment is not required prior to Cycle 1, but is required on cycle 1 day 1, cycle 1 day 15 and on day 1 of every subsequent cycle.

H. The pill calendar will be collected at the end of every cycle. The Pill Count/Diary is not required prior to Cycle 1, but is required every subsequent cycle.

I. As clinically indicated.

J. For Cycle 1, if the following tests/assessments occurred within 7 days of Day 1, they do not need to be repeated at this timepoint: H&P, Weight, Vital Signs; Performance Status; CBC w/diff, plt; Serum chemistry; Concomitant Medications.

K. Within 8 weeks of treatment assignment.

L. All subjects should have monthly Amsler grid tests and an initial ophthalmological examination performed at Screening by an ophthalmologist, which should include assessment of visual acuity, tonometry, fundoscopy (examination of both central and peripheral zones should be performed); where available, an Optical Coherence Tomography (OCT) should be performed. A follow-up ophthalmological examination should be performed as clinically necessary based on the findings of the monthly Amsler grid tests and clinical assessment. It is assumed that about 30% patients will require follow-up ophthalmological examinations.

When Central Serous Retinopathy (CSR)/Retinal Pigment Epithelial Detachments (RPED) is suspected, an OCT should be performed. Fluorescein angiography could be considered appropriate in conditions such as suspected Retinal Vein Occlusion (RVO). It is also recommended that color fundus photos or OCT images be obtained and stored in the subject's records for future reference. In subjects with suspected retinal pathology such as CSR or RVO, a consultation with a retina specialist should be considered.

Amsler grid testing will be administered by the treating physician or nurse on Day 1 of each 28-day cycle. Observation of wavy, broken or distorted lines, or a blurred/missing area of vision is equivalent to a positive Amsler grid test. For any positive Amsler grid test, subject should be referred for full ophthalmologic exam within 7 days. However, if the subject has an abnormal Amsler grid test at baseline (during Screening), then a repeat ophthalmic examination would be recommended only if, in the opinion of the investigator, there is a likelihood of significant change from the subject's baseline Amsler Grid test at Screening, or the subject has developed new clinical symptoms.

M. For subjects, treatment will be up-titrated or maintained based on phosphate level measured on Cycle 1 Day 15, and taking into account observed toxicity to that day, as described in Figure 1. The up-titrated dose would be given starting on Cycle 1 Day 15.

5. Drug Formulation and Procurement

This information has been prepared by the ECOG-ACRIN Pharmacy and Nursing Committees.

Availability

NO STARTER SUPPLIES MAY BE ORDERED. Subjects must be enrolled and assigned to the treatment subprotocol prior to submitting the clinical drug request to PMB.

Ordering instructions for Cycle 1:

Once a patient is registered to Arm K1, the site should request Cycle 1 supplies through OAOP consisting of the following:

- 2 bottles of 4 mg tablets and 2 bottles of 3 mg tablets

This quantity provides enough JNJ42756493 (erdafitinib) to complete Cycle 1 at either the:

- Starting dose of 8 mg on Days 1 - 28, or
- Starting dose of 8 mg on Days 1 – 14 and the up-titrated dose of 9 mg on Days 15 – 28.

Once it is determined whether the patient's dose will be up-titrated following completion of the Day 15 evaluation (including the patient's phosphate based on sections 3 and 4.1), a clinical drug request for the appropriate Cycle 2+ supplies should be submitted in OAOP per the usual ordering procedure.

Rev. Add16

Drug Ordering: NCI supplied agents may be requested by eligible participating Investigators (or their authorized designee) at each participating institution.

Pharmaceutical Management Branch (PMB) policy requires that drug be shipped directly to the institution where the patient is to be treated. PMB does not permit the transfer of agents between institutions (unless prior approval from PMB is obtained – see general information) The CTEP-assigned protocol number must be used for ordering all CTEP-supplied investigational agents. The eligible participating investigators at each participating institution must be registered with CTEP, DCTD through an annual submission of FDA Form 1572 (Statement of Investigator), NCI Biosketch, Agent Shipment Form, and Financial Disclosure Form (FDF). If there are several participating investigators at one institution, CTEP-supplied investigational agents for the study should be ordered under the name of one lead investigator at that institution.

Submit agent requests through the PMB Online Agent Order Processing (OAOP) application (<https://ctepcore.nci.nih.gov/OAOP>). Access to OAOP requires the establishment of a CTEP Identity and Access Management (IAM) account (<https://ctepcore.nci.nih.gov/iam/>) and the maintenance of an “active” account status, a “current” password, and an active person registration status.

NCI Supplied Agent(s) – General Information

Questions about drug orders, transfers, returns, or accountability should be addressed to the PMB by calling [contact] Monday through Friday between 8:30 AM and 4:30 PM Eastern Time or email [contact] anytime.

Drug Returns: All undispensed drug supplies should be returned to the PMB. When it is necessary to return study drug (e.g., sealed bottles remaining when PMB sends a stock

recovery letter), investigators should return the study drug to the PMB using the NCI Return Agent Form available on the NCI home page (<http://ctep.cancer.gov>).

Drug Accountability: The investigator, or a responsible party designated by the investigator, must maintain a careful record of the receipt, disposition, and return of agent received from the PMB using the NCI Investigational Agent Accountability Record Form for Oral Agents available on the NCI home page (<http://ctep.cancer.gov>). Maintain separate NCI Investigational Agent Accountability Records for each agent, strength, formulation and ordering investigator on this protocol.

Investigator Brochure Availability: The current versions of the IBs for PMB-supplied agents will be accessible to site investigators and research staff through the PMB Online Agent Order Processing (OAOP) application. Access to OAOP requires the establishment of a CTEP Identity and Access Management (IAM) account and the maintenance of an “active” account status, a “current” password, and active person registration status. Questions about IB access may be directed to the PMB IB coordinator at [contact].

